The VHA is the largest integrated health care system in the US, providing quality care at efficient prices for >5 million veterans across the country. According to VA estimates, there were about 22 million living US veterans in 2014.¹³

The size and structure of the VHA system differs from most private care organizations. The system includes:

- 153 medical centers;
- 136 nursing homes;
- 207 Vet Centers;
- 882 ambulatory care and community-based outpatient clinics;
- 45 residential rehabilitation treatment programs;
- 92 comprehensive home-based care programs;
- 13,000 physicians;
- nearly 55,000 nurses; and
- 9 million veterans.^{14,15}

[2018-7241 Study Identifier] Observational Study Protocol**Figure 4 VHA Data Elements**

VHA Database					
Medical SAS® Data		Decision Support System Data		Corporate Data Warehouse	Vital Status Data
Inpatient dataset	Outpatient dataset	Clinical NDE	Core NDE		

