
 • Acute Care: Inpatient (IP) stays for acute care at a medical center lasting ≥24 hours. • Extended Care: IP stays in VA community centers and care in VA nursing homes. 
Datasets within acute and extended care
 
 • Main: Hospital IP stay. Example variables include: 
 ○ 1^o/2^o diagnosis ○ Length of stay • Bed: IP stay under a specified physician service. Example variables include: 
 ○ 1^o/2^o diagnosis ○ Admission and discharge date ○ Length of stay • Procedure: Procedure in IP stay. Example variables include: 
 ○ Procedure date ○ ICD-9/10-CM codes • Surgery: Surgery in IP stay. Example variables include: 
 ○ Surgery date ○ ICD-9/10-CM codes 	
 • Event: One ambulatory/outpatient encounter by a patient. Example variables include: 
 ○ Encounter date ○ Procedure codes ○ Diagnosis codes 	
 • Laboratory results: Results for a specific list of laboratory tests, inpatient and outpatient. Example variables include: 
 ○ Service date ○ Result value ○ Test unit • Pharmacy: Prescription utilization and costs, inpatient and outpatient. Example variables include: 
 ○ Dispensing date ○ Quantity ○ Days supply ○ Cost 	
 • Discharge: Costs for inpatient services at discharge. Example variables include: 
 ○ Admission and discharge date ○ Length of stay ○ Total cost • Outpatient: Costs for outpatient services. Example variables include: 
 ○ Primary diagnosis ○ Visit date ○ Total cost 	
 • National repository of VHA administrative and clinical data. • Vital signs information such as blood pressure, height, weight, etc. • Example variables include: 
 ○ Vital type ○ Result ○ Date taken and entered 	
 • Provides mortality information. • One record per person who has received care or benefits, or enrolled in the VHA. • Provides enrolment information for each patient. • Example variables include: 
 ○ Death date ○ Race ○ Sex

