IP: inpatient stays; NDE: National Data Extracts; VA: Veterans Administration; 1^o/2^o: primary/secondary.

The VHA Medical SAS® datasets are national administrative data for VHA-provided health care used by veterans. The datasets are provided in SAS format by fiscal year (01OCT-30SEP). These data are extracted from the National Patient Care Database and maintained by the VHA Office of Information at the Austin Information Technology Center (the central repository for VA data).

VHA Medical SAS Inpatient Datasets

The Medical SAS Inpatient datasets cover the care received in acute, extended care settings. Within these categories, there are four datasets:

- main—a patient's inpatient stay (episode of care);
- bed section—a patient's inpatient stay under a specified physician treating for a specialty service;
- procedure—1 day's procedure during an inpatient stay; and
- surgery—1 day's surgery during an inpatient stay.

Inpatient variables describing each hospital admission include date, time, facility, and the primary diagnosis at admission. Discharge data include date, time, destination (eg, home, hospice,

[2018-7241 Study Identifier] Observational Study Protocol

community nursing home), type of discharge (eg, regular, transfer to another hospital, death), and length of stay (LOS).

VHA Medical SAS Outpatient Datasets

Each outpatient data record represents 1 date of service for 1 outpatient and includes the facility identifier, date, and time of visit. Visits on a single day to multiple clinics, laboratories, and treatment programs are reported.

Outpatient care is reported by diagnoses (ICD-9-CM and ICD-10-CM codes) and procedures (CPT codes), including dates and times.

Currently, there is 1 Medical SAS® dataset for outpatient care:

- Event: 1 ambulatory encounter (coded as Decision Support System [DSS] Identifier).

VHA Decision Support System

The VHA DSS is a managerial cost accounting system based on the commercial software Eclipsys®. The VHA must populate data elements required to allocate VHA costs to VHA products (goods and services provided during patient care). Towards that end, the VHA has modified Eclipsys to interact with VistA and other VA national databases. The VHA DSS was introduced in 1994 and fully implemented in all facilities by 1999.

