5.3. Study Population

5.3.1 Selection Criteria

Patient selection criteria for the U-500R Syringe Initiators [Index Event 1a]:

- Include patients who had ≥ 1 prescription claim for U-500R vial during the identification period (VHA and LCED: 01JAN2014-30JUN2017; Truven: 01APR2014-30SEP2017)—the first prescription claim for U-500R vial will be designated as index Event 1a (U-500R syringe initiation), and the date will be designated as the index date;
- Include patients who had ≥ 2 claims with an ICD-9/10-CM code (Appendix 1) for T2DM in any position (primary/secondary) at any time prior to the index date;
- Exclude patients who had both T1DM and T2DM, had no oral anti-diabetic drug (OADs; Appendix 1) other than metformin, and the ratio between the number of T1DM and T2DM claims > 0.5 at any time in the study period (VHA and LCED: 01APR2013-31MAR2018; Truven: 01JUL2013-30JUN2018);
- Include patients who were aged ≥ 18 years on the index date;
- Include patients who had continuous health plan enrollment with medical and pharmacy benefits for ≥ 9 months pre- and post-index event;
- Exclude patients with no evidence of insulin including U-500R (any type; Table 2) in the 9 months pre-index period (baseline);

[2018-7241 Study Identifier] Observational Study Protocol

- Exclude patients with ≥ 1 prescription claim for U-500R use in the 9 months pre-index period;
- Include patients who had ≥ 1 prescription claim for any insulin other than U-500R in the 9-month pre-index period;
- Include patients who had ≥ 1 HbA1c measurement within 90-day pre-index or 30-day post-index event;
- Include patients who had ≥ 1 HbA1c measurement after the 30-day post-index period at any time in the 9-months follow-up period;
 - Patients with ≥ 1 HbA1c measurement after the 30-day post-index and within 30 days prior to the end of the 9-months follow-up period will be flagged; and
 - Patients with ≥ 1 HbA1c measurement after the 30-day post-index and within 2 months prior to the end of the 9-months follow-up period will be flagged;
- Exclude patients who had ≥ 1 claim with a ICD-9/10-CM code (Appendix 1) for secondary diabetes, gestational diabetes, diabetes complicating pregnancy, childbirth, or puerperium, or non-clinical diabetes at any time during the 9-month baseline period;
- Exclude patients who had claims indicating pump use (Appendix 2) in the 9-month post-index (follow-up) period;

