6.4 Other Analyses**6.4.1 Outcomes Analyses**

All the analyses will be performed separately in VHA, linked Truven claims and EMR data, Truven claims database, and the pooled VHA and linked Truven claims and EMR data.

Pooling Multiple Databases

The VHA and linked Truven Claims with EMR databases will be pooled. To remove potential duplicate patient records from multiple data sources, probabilistic matching will be utilized. Potential duplicate patients across the databases will be identified by a STATinMED Research algorithm using age, sex, hospital admission date, hospital discharge date, and primary discharge diagnosis.^{23,24} Identified patients with the same information for the variables listed above will be assumed to be the potential duplicated patient and flagged in the pooled dataset. The rate of duplicate patients is expected to be low based on references and a previous study (<1%).²³ Duplicate patients can be potentially retained in the analytic file if the rate is low. After pooling, we will check if there are any potential duplicates across datasets. If the % will be small (<3%), we will not delete any duplicates because the impact to the final outcomes are considered minimal. If the % is significant (>3%), we will remove the duplicated records from the dataset that has the

[2018-7241 Study Identifier] Observational Study Protocol

larger sample size. Analyses will be conducted on each individual database as well as the pooled dataset.

Research Objective 1: Primary Objective 1Descriptive Analysis

All study variables including demographics, clinical characteristics, and treatment patterns of insulin (i.e., TDD, adherence, prescription fill rate, claim gaps, persistence, and concomitant medication use) will be analyzed descriptively before and after U-500R syringe initiation and U-500R Kwikpen initiation, and before and after U-500R device switch from syringe to Kwikpen.

Numbers and percentages will be provided for dichotomous and polychotomous variables. Means and standard deviations (SDs) will be provided for continuous variables. McNemar's test will be used to determine statistical significance of before and after values for categorical variables, and the paired t-test will be used to assess the statistical significance of before and after values in continuous variables.

Multivariate Analysis

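### In VHA data, the continuous-enrollment criterion does not show that the 9-month baseline was observable, so pre-index adherence, fills and hypoglycemia can be understated for veterans who reach VHA supply shortly before index

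*Protocol*

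**What the plan says.** Section 5.3.1 gives all three cohorts, in all databases, the same requirement: "Include patients who had continuous health plan enrollment with medical and pharmacy benefits", for at least 9 months before and after index. The note that closes the selection criteria relaxes the HbA1c rule for Truven claims but does not adapt the enrollment rule to VHA.

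Section 5.2 describes the VHA Medical SAS datasets as "national administrative data for VHA-provided health care used by veterans". In Figure 4, enrollment appears under Vital Status Data: "Provides enrolment information for each patient". The same entry is described as "One record per person who has received care or benefits, or enrolled in the VHA". Table 3 also names a VHA enrollment file, as the source of age, sex and race.

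On the baseline side, section 5.3.1 asks initiators for "≥ 1 prescription claim for any insulin other than U-500R in the 9-month pre-index period". Switchers need one U-500R vial fill in the same window. Every cohort needs two T2DM claims before index, with no minimum lead time. The baseline HbA1c may be taken from 90 days before to 30 days after index.

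In Table 3, PDC and average daily dose (ADD) divide by all days of the period. Fills are counted, and hypoglycemia per patient per year is reported, for the whole pre-index and post-index periods.

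**The concern.** In a commercial plan, enrollment with a pharmacy benefit is reasonable evidence that a fill would reach the claims file. In VHA it shows that a veteran is on the roll, not that VHA was the supplier. Time before a veteran began to use VHA looks the same as time without insulin and without hypoglycemia.

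The listed criteria do not screen this out. A veteran whose first VHA contact was a month before index can have the insulin fill, the two T2DM claims and the HbA1c, and is scored as having nine observed months. With unchanged behaviour, that patient's PDC, ADD, fills and hypoglycemia rate all rise at index.

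The VHA and pooled VHA/LCED results at stake are:
- the Objective 1 contrasts for adherence, ADD and fills, and the adherence mixed model;
- Objective 2a, where hypoglycemia is also the only protocol-defined adverse event (section 7.1);
- the Objective 2 mediation analysis, where PDC is the mediator and a significant time-adherence association leads to the next step.

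The Data Limitations text in section 5.2 does not mention care outside VHA. Yet section 6.4.1 foresees the same person in VHA and commercial data: "To remove potential duplicate patient records from multiple data sources, probabilistic matching will be utilized".

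**Working it through.** The protocol gives no figure on this point to reproduce. Table 4 holds feasibility counts only.

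**Inputs from the protocol.** The window is 9 months, taken as L = 274 days (30JUN2017 to 31MAR2018). Testing is two-sided at 0.05 without multiplicity adjustment (section 6.3). The VHA counts with at least two HbA1c values are 4,066 (Kwikpen) and 5,718 (vial), before most selection criteria.

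**Assumed inputs.** True PDC p = 0.70 on both sides of index; one fill per 30 days; an equal, constant hypoglycemia rate in all patients; SD of within-patient PDC change 25 to 35 points; share s of late entrants 1% to 20%.

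**One late entrant, visible for d days before index.** Observed pre-index PDC = p × d/L. Apparent hypoglycemia ratio = L/d.

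| d (days) | PDC pre | PDC post | Fills pre / post | Apparent hypoglycemia ratio |
|---|---|---|---|---|
| 30 | 0.08 | 0.70 | 1.0 / 9.1 | 9.1 |
| 60 | 0.15 | 0.70 | 2.0 / 9.1 | 4.6 |
| 90 | 0.23 | 0.70 | 3.0 / 9.1 | 3.0 |
| 180 | 0.46 | 0.70 | 6.0 / 9.1 | 1.5 |

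**Cohort mean.** If entry is uniform over baseline, half of the window is unobserved on average. PDC understatement = s × 0.5 × 0.70, and rate ratio = 1/(1 − s/2). With 60 visible days for every late entrant, replace 0.5 by 1 − 60/274 = 0.781.

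| s | PDC points, uniform | Rate ratio, uniform | PDC points, 60 days | Rate ratio, 60 days |
|---|---|---|---|---|
| 1% | 0.35 | 1.005 | 0.5 | 1.008 |
| 5% | 1.75 | 1.026 | 2.7 | 1.041 |
| 10% | 3.5 | 1.053 | 5.5 | 1.085 |
| 20% | 7.0 | 1.111 | 10.9 | 1.185 |

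**Share that alone gives an expected z of 1.96 in the paired t-test (uniform entry).** s = 1.96 × SD/√N ÷ 35 points.
- N = 1,000 (illustrative): 1.55/35 = 4.4% at SD 25, and 2.17/35 = 6.2% at SD 35.
- N = 5,718 (an upper limit, since most criteria are still to be applied): 0.65/35 = 1.9% and 0.91/35 = 2.6%.

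These shares ignore the extra variance that late entrants add, so they are slightly low.

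**The opposite case.** A veteran who has an HbA1c on day 31 and leaves VHA at day 60 meets every follow-up criterion. The observed post-index PDC is 0.70 × 60/274 = 0.15, the mirror image of a late entrant with 60 visible days.

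**What is not touched.** Observed TDD divides by days of supply, so unobserved time largely cancels. HbA1c is a single value near index and another in follow-up. Persistence is measured after index only. Truven-only and LCED-only analyses do not use VHA data.

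**The case against.** The strongest reply is that the protocol does not say how continuous enrollment with medical and pharmacy benefits is built in VHA. A one-record file can hold enrollment dates, Table 3 names a separate enrollment file, and the derivation could sit in an analysis plan that is not shown. This stands as a caution about implementation. It does not close the gap: eligibility is fixed here in health-plan terms, and exact enrollment dates would still not show that VHA supplied the insulin.

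A second reply is that the two-T2DM-claim rule and the required fill keep the baseline from being empty. They do limit the problem, but both can be met within weeks of index.

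Third, databases are analysed separately, so a VHA-only artefact might show as discordance with Truven (Objective 1) or LCED (Objective 2a). That helps, but the populations differ, so discordance would have more than one explanation.

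Fourth, a reader might infer that VHA results must rise by construction because follow-up is fully observed. The documents do not support this. Follow-up is anchored by a VHA fill and a later HbA1c, but day 31 is enough for that HbA1c, and leavers pull the other way. Nor do they support calling the pooled set VHA-dominated, because no LCED count is given.

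**Conclusion.** The enrollment criterion does not establish baseline observability in VHA, and late entrants can pass every listed criterion. For each of them, PDC, ADD, fills and hypoglycemia rate are understated before index and appear to rise. This part follows from the text.

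The effect on cohort results is not established in size or net direction. The documents give neither the share of late entrants nor the share of leavers. Under the stated assumptions the late-entry component runs from negligible (about 0.4 PDC points at a 1% share) to material (7 points and an 11% higher hypoglycemia rate at 20%). At the likely VHA sample sizes, a share of a few percent could by itself produce a significant paired test. The issue is confined to the VHA and pooled results for adherence, ADD, fills, hypoglycemia and the adherence mediator. It does not undermine the HbA1c or TDD contrasts.

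**What to change.** In section 5.3.1, define VHA baseline observability as at least one VHA outpatient pharmacy fill of any drug in the first 90 days of the 9-month baseline. The study data begin nine months before the first possible index date, so activity before baseline cannot be checked for everyone, whereas this can.

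Then:
- report how many otherwise eligible VHA patients fail the definition, which also gives a first measure of the unknown share;
- pre-specify that the VHA and pooled before/after results for PDC, ADD, fills and hypoglycemia, and the Objective 2 mediation analysis, are also given in patients who meet it (in the pooled set, the condition applies to VHA patients only);
- base the adherence and hypoglycemia conclusions on the two sets agreeing;
- add non-VHA care to the Data Limitations in section 5.2.

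This is better as a restricted analysis beside the main one than as a mandatory exclusion, because it corrects one side only and a fill of any drug does not prove that VHA supplied the insulin. Among those who meet it, unobserved lead time is at most about 90/274 = 33% of baseline.

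The cost is one flag on data already held, one extra analysis and a smaller restricted cohort. Residual dual use and leaving VHA after index remain, and should be stated as limitations.
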